10.6. Pregnancy Reporting

If a female patient or the partner of a male patient becomes pregnant while receiving study treatment or within 6 months after the completion of the last dose of study drug, a pregnancy report form should be completed and expeditiously submitted to the sponsor to facilitate outcome follow-up. Information on the status of the mother and child will be forwarded to the sponsor. Any premature termination of the pregnancy will be reported.

While pregnancy itself is not considered to be an AE or SAE, any pregnancy complication or elective termination of a pregnancy for medical reasons will be recorded as an AE or SAE.

An abortion, whether accidental, therapeutic, or spontaneous should be always reported as an SAE. Similarly, any congenital anomaly/birth defect in a child born to a patient exposed to the study drug should be recorded and reported as an SAE.

10.7. Poststudy Adverse Events

A poststudy AE or SAE is defined as any AE that occurs outside of the AE/SAE reporting period, as defined in [Section 10.3.1](#).

Investigators are not obligated to actively seek AEs or SAEs in former patients. However, if the investigator learns of any SAE, including a death, at any time after a patient has been discharged from the study, and he/she considers the SAE related to the study drug, the investigator will notify the sponsor.

10.8. Expedited Reporting to Health Authorities, Ethics Committees and Investigators

The sponsor will promptly assess all SAEs against cumulative study drug experience to identify and expeditiously communicate new safety findings to regulatory authorities, investigators, IRBs and IECs based on applicable legislation.

To determine the reporting requirements for individual SAEs, the sponsor will assess the expectedness of the SAEs using the [Pamiparib IB](#).

11. STATISTICAL CONSIDERATIONS AND ANALYTICAL PLAN

All data will be presented by Phase, summarized by arm and cohort in Phase 1b and by arm and expansion cohort in Phase 2. Most of the analysis methods described in this section are directed to the Phase 2 portion of the trial. However, they will be applied to the Phase 1 portion of data analyses whenever appropriate.

Details of the statistical analyses will be included in a separate statistical analysis plan (SAP).

11.1. Primary, Secondary and Exploratory Study Endpoints

Please refer to [Section 3](#) for a full listing of study endpoints.

11.2. Statistical Analysis

Hypothesis testing will be performed in Phase 2. In addition, descriptive statistics will be used in describing the antitumor activity and tolerability of the combination regimens in each Phase. CIs will be constructed to describe the precision of the point estimates of interest (eg ORR).

11.2.1. Analysis Set

- The Safety Analysis Set includes all patients who received any study treatment (pamiparib, RT, and/or TMZ). The Safety Analysis Set will be used for all efficacy and safety analyses.
- The Efficacy-evaluable Analysis Set includes patients in the Safety Analysis Set who had baseline and at least one post-baseline tumor assessment, unless discontinued treatment or study early due to clinical progression or death prior to tumor assessment.
- The DLT-evaluable Analysis Set includes patients who received ≥ 42 Gy of RT (Arms A and B) and $\geq 70\%$ of scheduled pamiparib (Arms A, B and C) and TMZ (Arms B and C) during the DLT assessment window with sufficient safety assessments. All patients who had a DLT event will be considered DLT-evaluable regardless of study treatment intensity.
- The PK Analysis Set includes all patients for whom valid pamiparib PK parameters can be estimated.

11.2.2. Patient Disposition

The number of patients enrolled, treated and discontinued from study drug, as well as those with major protocol deviations will be counted by arm. The primary reason for study drug discontinuation will be summarized according to the categories in the eCRF. The end-of-study status (alive, dead, withdrew consent, or lost to follow-up) at the data cutoff date will be summarized using the data from the eCRF.

Major protocol deviations will be summarized and listed by each category.

11.2.3. Demographics and Other Baseline Characteristics

Demographics and other baseline characteristics will be summarized by arm in the Safety Analysis Set using descriptive statistics. Continuous variables include age, weight, vital signs, time since initial tumor diagnosis, categorical variables include sex, age group (< 65 vs. ≥ 65 years), race, ECOG performance status, prior therapy for GBM, geographic region, and systemic corticosteroids at baseline.

11.2.4. Prior and Concomitant Therapy

Concomitant medications will be assigned an 11-digit code using the World Health Organization Drug Dictionary codes. Concomitant medications will be further coded to the appropriate Anatomical Therapeutic Chemical (ATC) code indicating therapeutic classification. Prior and concomitant medications will be summarized and listed by drug and drug class in the Clinical Study Report (CSR) for this protocol. Prior medications will be defined as medications that stopped before the first dose of study drug. Concomitant medications will be defined as medications that 1) started before first study treatment and were continuing at the time of first study treatment, or 2) started on or after the date of first study treatment up to 30 days after last study treatment. A listing of prior and concomitant medications will be included in the CSR.

11.2.5. Efficacy Analyses

Tumor assessments by investigators according to RANO will be used to calculate ORR, modified DCR (Arms A and B), DCR (Arm C), PFS, DOR, and CBR, as well as time-point estimate PFS-6m. OS and OS at 6 and 12 months (OS-6m and OS-12m) will be summarized in the efficacy analysis. An optional independent read of the MRI scans may be performed and will be analyzed in the same fashion.

11.2.5.1. Primary Efficacy Analysis

Phase 1b

As described in the protocol objectives, the trial is designed to establish the safety and tolerability of pamiparib in combination with RT and/or TMZ. Evidence of any antitumor activity will be documented and summarized for the Safety Analysis Set as secondary endpoints of the trial.

Phase 2 (Arms A and B)

Modified DCR is the primary efficacy endpoint in Arms A and B. It is defined as the proportion of patients with CR, PR, or SD as the response assessment at the EOT visit, as scheduled per protocol. Patients with no EOT tumor assessment, as scheduled per protocol (due to any reason), will be considered non-responders for modified DCR. Modified DCR of pamiparib combination therapy is assumed as 60% in the study population. The historical rate in a similar population is estimated as 40% (Riviera et al 2010).

The null and alternative hypotheses are set as follows:

H_0 : Modified DCR = 40%

H_a : Modified DCR > 40%

A binomial exact test will be performed for hypothesis testing in each arm separately in the Safety Analysis Set. If the obtained one-sided p-value is < 0.025, it will be concluded that pamiparib combination therapy showed a statistically significant increase of modified DCR compared to historical control. Therefore, the superiority of pamiparib combination therapy will be demonstrated in this arm.

Two-sided binomial exact 95% confidence interval (CI) of modified DCR will be constructed to assess the precision of the rate estimate.

The primary efficacy analysis will be conducted when mature response rate data have been observed, which will be determined by the sponsor.

Sensitivity analysis of modified DCR will be carried out in the Efficacy-evaluable Analysis Set.

Phase 2 (Arm C)

ORR is the primary efficacy endpoint in Arm C. ORR of pamiparib combination therapy is assumed as 25% in the study population. The historical rate in a similar population is estimated as 10% ([Chen et al 2013](#)).

The null and alternative hypotheses are set as follows:

H_0 : ORR = 10%

H_a : ORR > 10%

A binomial exact test will be performed within each expansion cohort of Arm C similarly to that described for Arms A and B.

11.2.5.2. Secondary Efficacy Analysis

Descriptive statistics will be used to summarize the secondary efficacy analysis.

DCR is defined as the proportion of patients with best overall response (BOR) of CR, PR, or SD. BOR is defined as the best response recorded from the start of study treatment until data cutoff or start of new anticancer therapy.

CBR is defined as the proportion of patients with BOR of CR, PR, or durable SD (SD \geq 24 weeks).

Exact 95% CIs will be calculated for the rate variables: ORR for patients with measurable disease at baseline, DCR, and CBR in the Safety Analysis Set.

PFS is defined as the time from the date of first study treatment to disease progression or death, whichever occurs first.

PFS censoring rule will follow [FDA Guidance for Industry, Clinical Trial Endpoints for Approval of Cancer Drugs and Biologics \(2007\)](#). Patients who have a clinical determination of progression should undergo an MRI, if possible, to correlate radiographic findings with the clinical findings.

Data for patients without disease progression or death at the time of analysis will be censored at the time of the last tumor assessment. Data for patients who are lost to follow-up prior to documented disease progression will be censored at the last tumor assessment date when the patient was known to be progression-free. Data for patients who started new anticancer therapy will be censored at the last tumor assessment date prior to the introduction of new therapy. More details will be given in the SAP.

DOR is defined as the time from the date of the earliest documented response to disease progression or death for any cause, whichever occurs earlier. Only responders will be included in the DOR calculation.

OS is defined as the time from the date of first study treatment to death of any cause.

Time-to-event variables PFS, DOR, and OS will be estimated using the Kaplan-Meier method in the Safety Analysis Set. Kaplan-Meier estimates of PFS, DOR, and OS will be plotted over time. Median PFS, DOR, and OS for each arm will be presented (if possible to estimate), along with their 2-sided 95% CIs using generalized Brookmeyer and Crowley method. The PFS-6m, OS-6m, and OS-12m, defined as the percentages of patients in the analysis population who remain alive and progression-free at 6 months (or alive at 6 or 12 months for OS-6m and OS-12m), will be estimated using Kaplan-Meier method along with the corresponding 95% CI constructed using Greenwood's formula. OS will be assessed by 6-month intervals until the last patient enrolled on the study had died.

Selected efficacy endpoints will be summarized in the Efficacy-evaluable Analysis Set as sensitivity analysis.

In Phase 2, modified DCR (in Arms A and B) and ORR (in Arm C) will be summarized in the specified subgroups: sex, age group (< 65 vs. ≥ 65), race, ECOG performance status (0 vs. ≥ 1), prior surgery status, baseline corticosteroid use, mutations, and geographic region. In addition, ORR (in Arm C) will be summarized by relapse status.

11.2.6. Pharmacokinetic Analyses

Population PK analysis may be carried out to include plasma concentrations from this trial in an existing model. PK parameters such as minimum observed plasma concentration (C_{min}) will be summarized, and additional PK parameters such as apparent clearance of the drug from plasma (CL/F) and area under the plasma concentration-time curve from zero to 24 hours post-dose (AUC_{0-24}) may be derived from the population PK analysis if supported by data.

Exposure-response (efficacy or safety endpoints) analysis may be carried out if supported by data. The results of the population PK and exposure-response analyses may be reported separately from the CSR. Details of the PK analyses will be provided in a separate SAP.

11.2.7. Exploratory Analyses

11.3. Safety Analyses

Safety will be assessed by monitoring and recording of all AEs graded by [CTCAE v4.03](#). Laboratory values, vital signs, physical examinations and ECG findings will also be used in determining the safety of the study treatment.

11.3.1. Extent of Exposure

Extent of exposure to each study treatment will be summarized in each arm descriptively as the number of cycles received (number and percentage of patients) in Arm C, duration of exposure (days), cumulative total dose received per patient (mg for pamiparib and TMZ and Gy for RT), dose intensity (mg/day for pamiparib and TMZ) and relative dose intensity.

The number (percentage) of patients requiring dose reductions, dose holds, and permanent drug discontinuation due to AEs will be summarized by arm. Frequency of dose reductions and study drug withholding will be summarized by categories.

Patient data listings will be provided for all dosing records and for calculated summary statistics.

11.3.2. Dose-limiting Toxicity

Dose-limiting toxicities in the DLT evaluation period will be summarized descriptively for each dose level in the DLT-evaluable population.

11.3.3. Adverse Events

Adverse Events will be coded using MedDRA Version 18.1 or higher and graded using NCI-CTCAE Version 4.03 or higher. A treatment-emergent adverse event (TEAE) is defined as an AE that had an onset date on or after first study treatment or was worsening in severity from baseline (pretreatment) up to 30 days following permanent study treatment discontinuation or initiation of new anticancer therapy, whichever occurs first. All TEAEs will be included in summary tables and in patient data listings.

The incidence of TEAEs will be reported as the number (percentage) of patients with TEAEs by system organ class (SOC) and preferred term (PT). A patient will be counted only once by the highest grade according to [NCI-CTCAE Version 4.03](#) or higher within an SOC and PT, even if the patient experienced more than one TEAE within a specific SOC and PT. The number (percentage) of patients with TEAEs will also be summarized by relationship to the study treatment. Treatment-related AEs include those events considered by the investigator to be related to study treatment or with missing assessment of the causal relationship. Serious AEs, deaths, TEAE of Grade ≥ 3 , related

TEAEs and TEAEs that led to study drug/treatment discontinuation, dose reduction or treatment delay will be summarized.

11.3.4. Laboratory Analyses

Clinical laboratory (eg, hematology and chemistry) values will be evaluated as specified in the SAP and collected in the EDC system. Collected values may be a subset of all the values obtained in the requested sampling, eg, a complete blood count with differential may be requested for the evaluation of neutrophils only. Analyzed laboratory values will be flagged and identified as those outside (above or below) the normal range.

Laboratory parameters that are graded in NCI-CTCAE [Version 4.03](#) will be summarized by NCI-CTCAE grade. Shift tables will be provided as appropriate.

11.3.5. Physical Examinations

Physical examination results collected in association with an AE will be listed and summarized.

11.3.6. Vital Signs

Specific vital signs, eg, blood pressure and temperature, will be summarized and listed. The change from baseline will also be presented.

11.3.7. Electrocardiogram

Electrocardiogram assessments will be performed as outlined in [Appendix 1](#). The percentage of patients with abnormal and clinically significant ECG findings will be presented.

11.4. Sample Size Consideration

Approximately 300 patients (60 in Phase 1b and 240 in Phase 2) may be enrolled. The actual sample size in Phase 1b will depend on the number of cohorts enrolled per arm.

In Phase 2, the sample size calculation is carried out using modified DCR in Arms A and B and ORR in each expansion cohort of Arm C.

- Assuming modified DCR of 60% in Arms A and B vs. 40% in historical control, the power of a binomial exact test is 0.874 in each arm when $n = 60$.
- Assuming ORR of 25% in Arm C vs. 10% in historical control, the power of a binomial exact test is 0.847 when $n = 60$ per expansion cohort.

With the above assumptions, the binomial exact 95% CI of modified DCR is (46.5%, 72.4%) in Arms A and B and the binomial exact 95% CI of ORR is (14.7%, 37.9%) in each expansion cohort of Arm C.

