In Phase 2, the sample size calculation is carried out using modified DCR in Arms A and B and ORR in Arm C.

- Assuming modified DCR of 60% in Arms A and B vs. 40% in historical control, the power of a binomial exact test is 0.874 in each arm when $n = 60$.
- Assuming ORR of 25% in Arm C vs. 10% in historical control, the power of a binomial exact test is 0.847 when $n = 60$ per expansion cohort.

With the above assumptions, the binomial exact 95% CI of modified DCR is (46.5%, 72.4%) in Arms A and B and the binomial exact 95% CI of ORR is (14.7%, 37.9%) in each expansion cohort of Arm C.

Interim Analysis:

A brief data summary will be performed once the Phase 1b dose escalation portion is completed. In Phase 2, an interim analysis will be implemented in each arm after approximately the first 20 patients in that arm complete ≥ 2 tumor assessments. This analysis is for futility only. No recruitment stop is planned for this interim analysis. If the conditional or predictive power of demonstrating the final efficacy is $< 10\%$, enrollment in this arm will be halted and safety and efficacy data will be further evaluated before making the decision of whether to stop the arm permanently. Otherwise, the enrollment will be continued to approximately 60 patients in this arm.

TABLE OF CONTENTS

SIGNATURES	2
Synopsis.....	3
TABLE OF CONTENTS	17
TABLE OF TABLES	22
TABLE OF FIGURES	22
LIST OF ABBREVIATIONS AND DEFINITIONS OF TERMS	24
1. INTRODUCTION.....	27
1.1. Biology of Glioblastoma	27
1.2. Imaging and Treatment of Glioblastoma.....	27
1.2.1. Overview and Key Data for Glioblastoma	27
1.2.2. Imaging of Glioblastomas	28
1.2.3. O ⁶ -methylguanine-DNA Methyltransferase Status and Treatment Response.....	29
1.2.3.1. Methylation of the O6-methylguanine-DNA Methyltransferase (MGMT) Gene Promoter	29
1.2.3.2. MGMT Methylation Status and Significance for Newly Diagnosed Glioblastoma	30
1.2.3.3. MGMT Methylation Status and Significance for Recurrent Glioblastoma	32
1.2.4. Treatment Toxicity	32
1.2.4.1. Toxicity of Dose-dense Temozolomide Regimens	32
1.3. Background on Poly (ADP-ribose) Polymerase Inhibitors and Pamiparib (BGB-290).....	33
1.3.1. Poly (ADP-ribose) Polymerase (PARP) and Pamiparib.....	33
1.3.2. PARP Inhibitors and Glioblastoma	33
1.3.3. PARP Inhibitors in Combination with Temozolomide or Radiation	34
1.3.4. Nonclinical Data for Pamiparib.....	36
1.3.4.1. Nonclinical Safety Data	36
1.3.4.2. Nonclinical Activity Data	37

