5 SAMPLE SIZE CONSIDERATIONS

Approximately 300 patients (60 in Phase 1b and 240 in Phase 2) were originally planned for enrollment. The actual sample size in Phase 1b depended on the number of Cohorts enrolled per arm and was 46 patients. The overall sample size was reduced during the study since the expansion cohorts were considered too large for this nonrandomized and nonregistrational study. The sample size in arm A expansion cohort is 40 and the sample size in arm C expansion cohort is 30. Overall the total number of patients enrolled in this study was 116.

Due to the reduction in sample size of the arm C expansion cohort, the analysis will not separate patients by MGMT status.

In Phase 2, the original sample size calculation was carried out using modified DCR in Arms A and B and ORR in each expansion cohort of arm C.

- 1) Assuming modified DCR of 60% in Arms A and B vs. 40% in historical control, the study is powered at ~82% to show 20% difference in modified DCR using a one-sided alpha of 0.025 when $n = 60$ per expansion cohort. Due to the reduction in actual sample size to 40 patients, assuming an observed modified DCR of 60%, the lower bound of the 80% exact confidence interval (CI) for the estimated modified DCR will exclude values less than 48%. The minimum observed modified DCR that has an 80% exact CI excluding 40% will be 53% (21 out of 40).
- 2) Assuming ORR of 25% in arm C vs. 10% in historical control, the study is powered at ~85% to show an 15% difference in ORR using a one-sided alpha of 0.025 when $n=60$ per expansion cohort. Due to the reduction in actual sample size to 30 patients, assuming an observed ORR of 25%, the lower bound of the 80% exact CI for the estimated ORR will exclude values less than 16%. The minimum observed ORR that has an 80% exact CI excluding 10% will be 20% (6 out of 30).

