8 CHANGES IN THE PROTOCOL PLANNED ANALYSIS

1. Sample size reduction: The overall sample size was reduced during the study since the expansion cohorts were considered too large for this non-randomized and non-registrational study.
2. All arm B expansion cohort related analysis and language are removed since it was decided not to enroll expansion cohort for arm B

3. Primary analysis will be performed on efficacy analysis set, not safety analysis set. No sensitivity analysis will be performed.

4. Exploratory objectives and endpoints in the protocol will not be explored in this SAP

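### The protocol's Arm A/B power of 0.874 is not that of the exact test it names (0.822), and the SAP gives ~82% as the original figure without noting the difference

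*Protocol*

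**What the plan says.** Protocol section 11.4 sets 60 patients per expansion cohort. For Arms A and B it states "Assuming modified DCR of 60% in Arms A and B vs. 40% in historical control, the power of a binomial exact test is 0.874"; the synopsis gives the same figure: "the power of a binomial exact test is 0.874 in each arm when" n = 60. For Arm C, at 25% against 10% and n = 60, "the power of a binomial exact test is 0.847 when" n = 60 per cohort.

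Section 11.2.5.1 defines the test. It is an exact binomial test in each arm separately, against a null modified DCR of 40%, with a strict criterion: "If the obtained one-sided p-value is < 0.025, it will be concluded that" the therapy improves on the historical rate.

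SAP section 5 looks back at that plan: "In Phase 2, the original sample size calculation was carried out using modified DCR in Arms A and B and ORR". For Arms A and B at n = 60 it then says "the study is powered at ~82% to show 20% difference in modified DCR using a one-sided alpha of 0.025". For Arm C it gives ~85%. It goes on to the reduced cohorts (40 in Arm A, 30 in Arm C) and describes them by 80% exact confidence intervals. For Arm C: "assuming an observed ORR of 25%, the lower bound of the 80% exact CI for the estimated ORR will exclude values less than 16" per cent.

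SAP section 8 lists departures from the protocol. Item 1 reads "Sample size reduction: The overall sample size was reduced during the study since the expansion cohorts were considered too large". It does not mention a changed power figure.

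**The concern.** Two documents describe one design, with the same rates, sample size and one-sided alpha, and give two powers: 0.874 and ~82%. The SAP is written for protocol version 2.0, which is the version that prints 0.874, yet it labels ~82% as the original calculation. Both cannot be the power of the exact test.

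If the protocol figure is the wrong one, it understates the chance of missing the assumed effect in Arms A and B: 1 − 0.874 = 12.6% as implied, against 1 − 0.822 = 17.8%. Anyone reporting the planned design would have to choose between the two figures with no explanation in either document.

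The Arm C bound raises a separate, smaller doubt. An observed rate of 25% in 30 patients means 7.5 responders, so the bound attached to it must belong to some other count, which is not stated.

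**Working it through.** **Inputs.** Null 0.40, alternative 0.60, exact test in each arm, one-sided p < 0.025 (protocol 11.2.5.1); n = 60 and stated power 0.874 (protocol 11.4). For Arm C: 0.10, 0.25, n = 60, stated power 0.847 (protocol 11.4); n = 30 and the 16% bound (SAP 5).

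**Check that the method matches the plan.** The 95% Clopper-Pearson intervals in protocol 11.4 reproduce: 36/60 gives 46.5% to 72.4%, and 15/60 gives 14.7% to 37.9%.

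**Power, Arms A and B.** Take the smallest r with P(X ≥ r | n = 60, p = 0.40) < 0.025. The power is P(X ≥ r | n = 60, p = 0.60).

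| Reject at | Alpha (p = 0.40) | Power (p = 0.60) |
|---|---|---|
| ≥ 31 | 0.0445 | 0.925 |
| ≥ 32 | 0.02503 | 0.882 |
| ≥ 33 | 0.01328 | 0.822 |
| ≥ 34 | 0.0066 | 0.746 |

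The cut-off is 33 and the power is 0.822. The difference from the protocol is 0.874 − 0.822 = 0.052. The possible powers at n = 60 are discrete, and 0.874 falls between those for 32 and 33, so no choice of alpha produces it.

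**Where 0.874 might come from.** Approximations at n = 60 and one-sided 0.025 come close:

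- Normal: Φ[(0.20√60 − 1.96√0.24)/√0.24] = 0.885; with continuity correction 0.858.
- Arcsine: Φ[2√60(arcsin√0.6 − arcsin√0.4) − 1.96] = 0.877.
- Mid-p or two-sided exact test: both reject at 32 and give 0.882.

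None equals 0.874, and none is the test named.

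A futility stop after 20 patients was also tried, with power = Σ P(X₁ = x) P(X₂ ≥ r − x) over x above the stopping count, where X₁ is the count in the first 20 patients and X₂ that in the other 40. A final cut-off of 32 with a stop at 7/20 or fewer gives 0.873. The same construction in Arm C (final cut-off 12) gives 0.852 with a stop at 0/20 and 0.843 with a stop at 1/20 or fewer, so it does not yield 0.847.

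**Power, Arm C.** P(X ≥ 11 | 60, 0.10) = 0.0342 and P(X ≥ 12 | 60, 0.10) = 0.0146, so the cut-off is 12. Power = P(X ≥ 12 | 60, 0.25) = 0.852. The stated 0.847 is 0.5 points low; the SAP's ~85% agrees with the exact value.

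**80% exact lower bounds in SAP 5.** The bound is the 10th percentile of Beta(x, n − x + 1).

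| Observed | Rate | Lower bound |
|---|---|---|
| 7/30 | 23.3% | 13.5% |
| 7.5/30 (interpolated) | 25% | 14.8% |
| 8/30 | 26.7% | 16.2% |
| 5/30 | 16.7% | 8.3% |
| 6/30 | 20% | 10.9% |
| 20/40 | 50% | 38.8% |
| 21/40 | 52.5% | 41.2% |
| 24/40 | 60% | 48.6% |

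The 16% belongs to 8/30. The minimum counts in the SAP are right: 6/30 is the first to exclude 10%, and 21/40 the first to exclude 40%. The 48% for 24/40 is true as worded.

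**The case against.** The strongest reply is that little depends on this. The 60-patient design is gone: Arm A expansion is 40, Arm C is 30, and Arm B expansion was not opened. SAP 6.4.1 drops formal testing for Arms A and B, so the test in question will not be run. The SAP already carries the correct power, and 0.822 is still above 80%, so 60 patients was not too few by that common benchmark. All of this stands and limits the weight of the point.

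The gap is also a near miss. A cut-off of 32 fails the 0.025 criterion by 0.00003. Had it been admitted, power would be 0.882 and the protocol's figure 0.8 points too low. But section 11.2.5.1 requires p strictly below 0.025, and 0.874 would be wrong either way.

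A futility adjustment comes close (0.873), but no stopping count is written, section 11.4 mentions no such adjustment, and the Arm C figure does not follow from it.

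The Arm C power difference is half a point in the conservative direction and would not merit a comment alone. On the 16% bound, 7.5 rounds up to 8, and that may be what was done; this is an inference. A Wilson interval at 25% also gives a lower limit of 16.3%, but the SAP says exact. Against the interpolated value at 25% (14.8%) the excess is about 1.2 points rather than 2.5.

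Finally, SAP section 8 is a list of changed analyses, and a corrected power at a superseded sample size need not appear there. The label in SAP section 5 is the better evidence that the difference went unremarked.

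**Conclusion.** The concern holds. For 60% against 40% at n = 60, with the exact binomial test and one-sided p < 0.025, the power is 0.822. The protocol's 0.874 overstates it by 5.2 points, and how it was obtained is not documented. SAP section 5 has the right value but presents it as the original one without acknowledging the protocol's figure. The Arm C power (0.847 stated, 0.852 exact) is a minor discrepancy. The 16% lower bound is right for 8/30, is 2.5 points too high for 7/30 (16% − 13.5%), and cannot apply to exactly 25% of 30.

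The result rests only on the rates, sample size and decision rule printed in the protocol, including the strict inequality. The consequence is confined to these statements: thresholds, sample sizes and planned analyses are unaffected.

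**What to change.** Add one clause to SAP section 5, or to item 1 of section 8: the exact-test power at n = 60 is 0.822 for Arms A and B (rejection at 33/60 or more), replacing the 0.874 in protocol section 11.4. The Arm C value of 0.852, in place of 0.847, can go in the same clause.

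In SAP section 5, item 2, tie the bound to attainable counts: with 8/30 responders (27%) the 80% exact lower bound is 16%; with 7/30 (23%) it is 13%. Leave the 21/40 and 6/30 thresholds as they are.

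The cost is one clause and one sentence. Correcting section 11.4 and the synopsis directly is the alternative, but protocol section 12.3.1 requires every protocol modification to be submitted to the authorities and ethics committees. That is hard to justify for a superseded design, so the SAP note is the proportionate choice unless the protocol is being amended for another reason.
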